## Study design

This is a Phase I, open-label, 2-period fixed sequence design study to evaluate the interaction of AZD9291 with omeprazole in approximately 50 healthy, adult male volunteers. The study will be performed at up to 2 sites in the USA.

Volunteers will receive Treatment A in Period 1 and Treatment B in Period 2. The dose of AZD9291 in Period 1 and the dose of AZD9291 in Period 2 will be separated by a washout of at least 21 days (the washout will not be more than 5 weeks).

Treatment A: On Days 1 through 4, omeprazole will be administered in the morning

after a 10-hour fast with 240 mL of water 1 hour before eating breakfast. On Day 5, omeprazole will be administered together with AZD9291 with 240 mL of water following an overnight fast of 10 hours and the

volunteers will remain fasting from food until 4 hours postdose.

Treatment B: Volunteers will receive AZD9291 in the morning on Day 1 with 240 mL

of water following an overnight fast of 10 hours. Volunteers will remain

fasting from food after dosing until 4 hours postdose.

The study will consist of up to 15 visits depending on whether the final pharmacokinetic (PK) sample of Period 1 is collected as the predose PK blood sample for Period 2 or whether a separate visit is required for the predose PK blood sample. The screening visit (Visit 1) will be conducted within 28 days of Visit 2. Following full written informed consent, healthy male volunteers will be enrolled into the study and screened for eligibility.

In Period 1 the volunteers will report to the clinic on Day -1 (the day prior to first dose of omeprazole) and remain resident until the 48-hour postdose (relative to AZD9291 administration on Day 5) monitoring and evaluations have been performed on Day 7. The volunteers will return to the clinic for outpatient visits on Days 8, 10, 12, 14 and 19. The Day 26 postdose assessments may be used as the Day -1 predose assessments for Period 2 if an exact 21-day washout is used between AZD9291 doses in Period 1 and Period 2. AZD9291 concentrations obtained over the first 72 hours in Period 1 will be evaluated to determine if exposure limit criteria for a given volunteer and/or a group of dosed volunteers are met or exceeded prior to AZD9291 administration in Period 2. Volunteer(s) exceeding PK exposure limits will be withdrawn.

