In Period 1 the volunteers will report to the clinic on Day -1 (the day prior to first dose of omeprazole) and remain resident until the 48-hour postdose (relative to AZD9291 administration on Day 5) monitoring and evaluations have been performed on Day 7. The volunteers will return to the clinic for outpatient visits on Days 8, 10, 12, 14 and 19. The Day 26 postdose assessments may be used as the Day -1 predose assessments for Period 2 if an exact 21 day washout is used between AZD9291 doses in Period 1 and Period 2. AZD9291 concentrations obtained over the first 72 hours in Period 1 will be evaluated to determine if exposure limit criteria for a given volunteer and/or a group of dosed volunteers are met or exceeded prior to AZD9291 administration in Period 2. Volunteer(s) exceeding PK exposure limits will be withdrawn.

[figure not shown]
In Period 2 the volunteers will report to the clinic on Day -1 and remain resident until 48-hour postdose (relative to AZD9291 administration) monitoring and evaluations have been performed on Day 3. The volunteers will return to the clinic for outpatient visits on Days 4, 6, 8, 10, 15 and 22. A final follow-up visit (Visit 15) will be performed 7 to 14 days after the last PK blood sample in Period 2.

Safety assessments will include monitoring of AEs and concomitant medications; clinical laboratory tests (hematology, clinical chemistry and urinalysis); measurement of vital signs (supine blood pressure and pulse); ECGs; physical examinations; screening for drugs of abuse, alcohol and cotinine; and ophthalmologic examinations.

Blood samples for the determination of AZD9291 and metabolite (AZ5104 and AZ7550) concentrations will be collected prior to dosing of AZD9291 and serially postdose for 21 days in each treatment period. The PK profile from 0 to 72 hours post AZD9291 dose will be assessed after Period 1 and Period 2 and any volunteer with exposures exceeding the PK limits (Section 5.8) will be withdrawn and may be replaced if required to ensure 40 evaluable volunteers complete. For a volunteer to be evaluable the volunteer must have completed the required PK collections for both study periods without important protocol deviations and events.

The overall study flow chart and study is presented in Figure 1.

Figure 1 Study flow chart

- a Volunteers will be admitted into the clinic on Day -1 in both periods.

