- b Each AZD9291 dosing day will be a minimum of 21 days (504 hours) apart (the washout will not be more than 5 weeks).
- Note where the washout is 21days, Day 26of Period 1 will coincide with Day-1 of Period 2 (ie, the 504-hour postdose PK assessment from Period 1 will be collected on Day -1 of Period 2); where the washout is slightly longer volunteers may return to the clinic for an additional visit prior to admission to Period 2 to allow for the collection the PK sample.
- Treatment A: On Days 1 through 4, omeprazole will be administered in the morning after a 10-hour fast with 240 mL of water 1 hour before eating breakfast. On Day 5, omeprazole will be administered together with AZD9291 with 240 mL of water following an overnight fast of 10 hours and the volunteers will remain fasting from food until 4 hours postdose.
- e Treatment B: Volunteers will receive AZD9291 in the morning on Day 1 with 240 mL of water following an overnight fast of 10 hours. Volunteers will remain fasting from food after dosing until 4 hours postdose.

Table 1 Study plan

Visit	1	2 t	o 7		8	to 13	14
Assessment	Screening	Period 1 ≥21 day washout b		Period 2		Follow up visit	
Day	-28 to -2	-1	1 to 26		-1	1 to 22	
Residential period (Day)		X	1 to 7		X	1 to 3	
Nonresidential visit	X		X l			$\mathbf{X}^{\mathbf{l}}$	X
Informed consent	X						
Informed consent, pharmacogenetic m	X						
Demography	X						
Inclusion/exclusion criteria	X	X					
Medical history	X	X					
Clinical laboratory tests a	X	X	X		X	X	X
Serology	X						
Height and body mass index	X						
Weight	X	X			X		
Urinary drug, alcohol breath test, and cotinine screen c	X	X			X		
Ophthalmological assessment	X d						
Physical examination e	X	X			X		X
Vital signs (supine blood pressure and pulse) f	X	X	X		X	X	X
12-lead electrocardiogram g	X	X	X		X	X	X
AZD9291 administration h			X			X	
Omeprazole administration i			X				
AZD9291 PK blood sampling j			X		X	X	X
Concomitant medications	X	X	X	X	X	X	X
Adverse event recording k		X	X	X	X	X	X

a Clinical laboratory tests: Period 1, Days -1, 5 (pre-dose), 7, 12 and 19; Period 2; Days -1, Days 3, 8, 15 and 22.

- b Each AZD9291 dosing day will be a minimum of 21 days (504 hours) apart (the washout will not be more than 5 weeks).

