This study will be conducted in healthy male volunteers aged 18 to 55 years in order to avoid interference with the study results from disease processes and other drugs. The selection criteria are defined such that volunteers selected for participation in the study are known to be free from any significant illness. There is no observed gender difference in patient data; therefore, there is no reason to expose women to AZD9291. Safety monitoring and stopping criteria have been developed based upon knowledge of EGFR-TKI class effects, preclinical toxicology, and emerging clinical safety data with AZD9291 to ensure the safety of participating volunteers.

Blinding is not considered necessary, as the primary objective is plasma AZD9291 concentration-time profiles and the resulting PK parameters are objective measurements. Thus, the risk of bias is minimal.

A sequential design has been selected to optimally manage volunteer visits considering the long treatment period and frequency of outpatient visits for PK collections and to enhance the safety of this study relative to the implemented stopping criteria. Since the study starts with the combination treatment which could result in lower AZD9291 exposure (if an effect is

observed), volunteers showing high exposure may be withdrawn prior to administration of AZD9291 alone which could result in a larger number of volunteers exposed to the investigational product (IP). This study is designed using the principles embodied in the United States Food and Drug Administration guidance on drug interaction studies (Guidance for Industry February 2012).

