# 5.8 Discontinuation of investigational product

Volunteers may be discontinued from IP in the following situations:

- Volunteer decision. The volunteer is at any time free to discontinue treatment, without prejudice to further treatment
- Adverse event
- Severe non-compliance to study protocol
- Development of any study-specific safety criteria for discontinuation (see Sections 6.3.5)
- Exceeding PK limit criteria
  - Individual measurement of AZD9291 AUC(0-72) greater than 7005 nM·h

- If an individual measurement of AZD9291 AUC(0-72) is 5000 nM·h or more, then the Investigator in consultation with the Sponsor will decide whether the volunteer may continue in the study or be withdrawn.
- If the group mean AUC(0-72) exceeds 5230 nM·h in Period 1, then volunteers with the highest exposures will be withdrawn from the study until the group mean AUC(0-72) is below 5230 nM·h before Period 2 commences. (Note: this applies to each block [cohort] of volunteers, where not all 50 volunteers are enrolled at the same time.)

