## 5.8.1 Procedures for discontinuation of a subject from investigational product

A volunteer that decides to discontinue IP will always be asked about the reason(s) and the presence of any AEs. If possible, they will be seen and assessed by an investigator(s). Adverse events will be followed up (See Sections 6.3.3 and 6.3.4).

If a volunteer is withdrawn from study, see Section 5.9.

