## 5.9 Withdrawal from study

Volunteers are at any time free to withdraw from study (IP and assessments), without prejudice to further treatment (withdrawal of consent). Such volunteers will always be asked about the reason(s) and the presence of any AEs. If possible, they will be seen and assessed by an investigator. Adverse events will be followed up (See Sections 6.3.3 and 6.3.4).

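### Section 3.1 applies PK-limit withdrawal, with optional replacement, to the Period 2 profile, when no AZD9291 dose is left to withhold

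*Protocol*

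**What the plan says.** The exposure stop is described in several places in the protocol.

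- **Synopsis, Study design, and the matching text of Section 3.1.** Concentrations over the first 72 h of Period 1 are used to see whether the limits "are met or exceeded prior to AZD9291 administration in Period 2".
- **Section 3.2.** The fixed sequence is justified partly because "volunteers showing high exposure may be withdrawn prior to administration of AZD9291 alone".
- **Section 5.8.** The list opens with "Volunteers may be discontinued from IP in the following situations". It gives an individual AUC(0-72) limit of 7005 nM·h and a case-by-case decision from 5000 nM·h, neither tied to a period. It also gives a group-mean limit of 5230 nM·h, which applies to Period 1 and must be resolved "before Period 2 commences".
- **Section 3.1, paragraph on PK sampling.** The 0-72 h profile "will be assessed after Period 1 and Period 2 and any volunteer with exposures exceeding the PK limits (Section 5.8) will be withdrawn". Such a volunteer may be replaced if that is needed to reach 40 evaluable men.

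On what withdrawal means, Section 5.8.1 says "If a volunteer is withdrawn from study, see Section 5.9". Section 5.9 says volunteers are "free to withdraw from study (IP and assessments"), and ties this to withdrawal of consent.

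**The concern.** A stopping limit is useful only while there is something to stop. The synopsis (Duration of treatment) gives one 80 mg AZD9291 dose on Period 2 Day 1 and nothing after it. By the time a Period 2 0-72 h profile exists, both doses have been taken. The Section 3.1 clause still makes withdrawal mandatory at that point and allows a replacement.

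The clause cannot reduce that man's exposure. If a site follows it, it can have only two effects. It can end scheduled observation in the men with the highest exposure to AZD9291 alone, or it can bring in a new healthy man for up to two further AZD9291 doses. The second sits badly with the aim in Section 1.3.1 of keeping the number of exposed volunteers small.

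Late safety visits matter here. According to Section 1.3.1, the only event judged related to AZD9291 in the earlier healthy-volunteer study was an ALT rise that peaked on Day 15 after a single dose.

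**Working it through.** **1. The planned power reproduces.** Inputs from Section 12.3: within-subject CV 23%, true ratio 0.95, 40 evaluable men, 90% CI within 80-125%.

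- σw = √ln(1 + 0.23²) = 0.227. The SE of the mean log difference is σw·√(2/n), with n − 1 degrees of freedom.
- Exact power of the two one-sided tests at n = 40 is 95.3% per parameter. The product for two parameters, taken as independent, is 0.953² = 90.9%. The protocol states 95% and 90%.
- Enrolment: 40/(1 − 0.20) = 50, as stated.

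**2. What is scheduled after 72 h in Period 2 (Table 2).**

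- PK: 19 samples per period (2 × 19 = 38, matching Table 4). Five come after 72 h: 120, 168, 216, 336 and 504 h.
- Safety: vital signs, ECG and laboratory tests at 168, 336 and 504 h (Days 8, 15 and 22).
- Follow-up: Visit 15, 7 to 14 days after the last PK sample (Section 3.1).

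**3. When would the clause act?** Two readings are open.

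- *After Day 22.* Table 1 shows Period 2 as Days 1 to 22, so this is the more natural sense. No PK sample is lost, but Visit 15 is still to come.
- *Once the 72 h data are known.* In Period 1 with an exact 21-day washout this must be the sense: "the 504-hour postdose PK assessment from Period 1 will be collected on Day -1 of Period 2", yet the group check has to be finished before that period starts. What forces this is the coming Period 2 dose. Period 2 has no such deadline, so the argument does not carry over by itself.

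**4. How much AUC would rest on extrapolation if sampling did stop early.** Half-life in healthy volunteers is 52.72 h (range 32.5 to 72.0 h, capsule; Section 3.2). Assumption: one-compartment oral model with ka = 0.4/h. Share beyond time T = (ka·e^(−kT) − k·e^(−ka·T))/(ka − k), with k = ln 2/half-life.

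| Last sample | Share at 52.72 h | Range, 32.5 to 72.0 h |
|---|---|---|
| 72 h | 40% | 23-51% |
| 120 h | 21% | 8-32% |
| 168 h | 11% | 3-20% |
| 216 h | 6% | 1-13% |
| 336 h | 1% | 0-4% |
| 504 h | 0.1% | 0-0.8% |

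Losing all five late samples needs a decision within 120 − 72 = 48 h of the 72 h sample. The protocol gives no assay turnaround. If sampling reaches 168 to 216 h, AUC is probably still estimable. Cmax and AUC(0-72) are not touched.

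**5. Scale of the effect on the primary comparison, complete pairs only.** The SD of one log pair difference is √2 × 0.227 = 0.321. Dropping one of 40 pairs whose difference lies z SD from the mean moves the mean by z × 0.321/39. That is 0.0082 for z = 1 (about 0.8% on the ratio) and 0.0165 for z = 2 (about 1.7%). Power per parameter with 39 pairs is 94.9%.

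These are sizes per lost pair, not predictions. The protocol gives neither AUC(0-72) at 80 mg nor a between-subject CV, so the number of men over a limit cannot be worked out. The planned mixed model would also keep the Period 1 value of a man with no Period 2 AUC.

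**The case against.** The strongest reply is that the extra words are merely redundant. The assessment after Period 2 most naturally follows Day 22, when all PK samples are in. The Section 5.9 wording about assessments describes a volunteer's own withdrawal of consent. The opening of Section 5.8 concerns stopping IP, which does not in itself stop sampling. Section 3.2 expects exposure to stay below the limits. Section 12.2.1 keeps data up to discontinuation and does not restrict analyses to complete cases. Detected problems are covered: extra assessments for safety (Section 6), follow-up of unresolved adverse events (6.3.3), monitoring of significant laboratory deviations (6.3.5) and of potential Hy's Law cases (Appendix D). A man who completed sampling also creates no need for a replacement.

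Most of this stands, and it rules out two stronger readings that a reader might infer.

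- *That the protocol orders sampling to stop at 72 h in Period 2.* It does not. That needs early timing carried over from Period 1 and the consent wording of Section 5.9 applied to a PK-limit withdrawal.
- *That the clause biases the AUC ratio upward by removing high values under AZD9291 alone.* At best this would hold if AUC were wholly missing in complete pairs. Extrapolation error has no fixed sign, and the mixed model does not drop the man's other period.

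The reply does not show that the clause is harmless or corrected elsewhere. The group rule in Section 5.8 itself speaks of withdrawal from the study, not only from IP. Nothing says that scheduled visits continue after a PK-limit withdrawal. Even withdrawal after Day 22 precedes Visit 15. The safeguards listed act mainly on abnormalities already found; a new, silent one needs a scheduled test to be seen.

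**Conclusion.** The point holds as a minor defect in the design text. Section 3.1 makes withdrawal mandatory, with optional replacement, on Period 2 data when no AZD9291 dose remains. That contradicts the stated purpose of the stop and protects no one. Acted on, it could cost scheduled PK or safety visits, or at least the follow-up visit, in the most exposed men, or lead to needless exposure of a replacement. Which of these would happen depends on how a site reads the timing and the word withdrawn, and the protocol settles neither.

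The effect on the primary AUC and Cmax conclusion is near zero, and no direction of bias is established. This rests on the protocol's own expectation that the limits will not be exceeded, and on the small effect of any one lost pair.

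**What to change.** In Sections 3.1 and 5.8:

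1. Limit PK-limit withdrawal and replacement to Period 1 data.
2. State that a volunteer over a limit in Period 2 completes all PK sampling to 504 h and all safety visits including follow-up, stays in the primary analysis, and is not replaced for that reason.
3. State that a volunteer stopped on Period 1 data receives no Period 2 dose but completes the scheduled Period 1 safety visits and follow-up. Without this, the same uncertainty about the meaning of withdrawal remains for Period 1.

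The cost is a few sentences. No volunteers are added, the visits and samples are those already scheduled, and the sample size and power are unchanged. No exposure protection is lost, because the Period 1 check still acts before the only dose it can prevent.

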## 3.2 Rationale for study design, doses and control groups

An 80 mg AZD9291 dose has been selected, since it is the expected therapeutic dose in a patient population and most scientifically relevant to evaluate the effect of changes in gastric pH on AZD9291 pharmacokinetics. Based on preliminary data from Study D5160C00005 in which a 20 mg AZD9291 dose was administered as capsule, solution, and tablet formulations, AZD9291 exposure following an 80 mg dose is not expected to exceed the exposure limits set for healthy volunteers. In case of a potential drug interaction with omeprazole, only a decrease in exposure would be expected based on the physiochemical characteristics of AZD9291. Hence, AZD9291 exposure during coadministration of omeprazole is not expected to exceed the exposure limits.

Pharmacokinetic (PK) data show that AZD9291 was slowly absorbed following oral dosing, with patients (D5160C00001) and healthy volunteers (D5160C00005) generally showing a lag time of up to 4 hours in the AZD9291 plasma concentration versus time profile following single dose administration. In healthy volunteers, after a single oral dose of AZD9291 administered as the capsule, the observed apparent mean (minimum-maximum) terminal half-life ( $t_{1/2}$ ) was 52.72 (32.5 to 72.0) hours.

After single administration of AZD9291 to healthy volunteers as the capsule, AZ5104 and AZ7550 were slowly produced with the time to reach maximum plasma concentration (tmax) ranging from 6 to 72 hours, with a plateau in concentration observed for 3 to 4 days after dosing. The concentration of AZ5104 and AZ7550 then declined monoexponentially: AZ5104 with a similar t½ to AZD9291, and AZ7550 displaying a slightly longer t½. The observed apparent mean (minimum-maximum) t½ was 48.92 (31.1 to 65.2) and 73.21 (52.4 to 105) hours for AZ5104 and AZ7550, respectively. For this reason, a washout of at least 21 days between the AZD9291 doses in Period 1 and Period 2 has been selected for this study (the washout will not be more than 5 weeks).

This study will be conducted in healthy male volunteers aged 18 to 55 years in order to avoid interference with the study results from disease processes and other drugs. The selection criteria are defined such that volunteers selected for participation in the study are known to be free from any significant illness. There is no observed gender difference in patient data; therefore, there is no reason to expose women to AZD9291. Safety monitoring and stopping criteria have been developed based upon knowledge of EGFR-TKI class effects, preclinical toxicology, and emerging clinical safety data with AZD9291 to ensure the safety of participating volunteers.

Blinding is not considered necessary, as the primary objective is plasma AZD9291 concentration-time profiles and the resulting PK parameters are objective measurements. Thus, the risk of bias is minimal.

A sequential design has been selected to optimally manage volunteer visits considering the long treatment period and frequency of outpatient visits for PK collections and to enhance the safety of this study relative to the implemented stopping criteria. Since the study starts with the combination treatment which could result in lower AZD9291 exposure (if an effect is

observed), volunteers showing high exposure may be withdrawn prior to administration of AZD9291 alone which could result in a larger number of volunteers exposed to the investigational product (IP). This study is designed using the principles embodied in the United States Food and Drug Administration guidance on drug interaction studies (Guidance for Industry February 2012).

## 4. SUBJECT SELECTION CRITERIA

Investigator(s) should keep a record, the volunteer screening log, of volunteers who enter prestudy screening.

Each volunteer should meet all of the inclusion criteria and none of the exclusion criteria for this study. Under no circumstances can there be exceptions to this rule.

#### 4.1 Inclusion criteria

For inclusion in the study volunteers must fulfil the following criteria.

- 1. Provision of signed and dated informed consent prior to any study-specific procedures.
- 2. Healthy male volunteers aged 18 to 55 years. (Healthy as determined by medical history, physical examination, laboratory parameters, ECG, and eye examination performed before the first administration of IP.)
- 3. Body mass index between 19 and 30 kg/m^2, and body weight between 50 kg and 100 kg, inclusive
- 4. Veins suitable for cannulation or repeated venepuncture.
- 5. Volunteers must be willing to use reliable methods of contraception (condom and spermicide), even if their partners are postmenopausal, surgically sterile, or using an effective hormonal method of contraception or intrauterine coil. In addition, volunteers must agree to continue to take similar contraceptive precautions and avoid sperm donation for 6 months after the last administration of AZD9291.
- 6. Be willing and able to comply with study procedures, restrictions, and requirements.

